Rationale: The immune monitoring will be limited to one year after thymus transplantation. Cumulative data on the previous thymus transplant recipients (60 subjects from 5 protocols 'Thymus Transplantation in Complete DiGeorge, Protocol #668'; 'Thymus Transplantation and Immunosuppression, #884'; 'Parathyroid and Thymus Transplants in DiGeorge Syndrome, #931'; 'Dose Study of Thymus Transplantation in DiGeorge Anomaly, IND #9836, #932'; and, 'Phase I/II Trial of Thymus Transplantation with Immunosuppression, #950')

support the change from long term monitoring to one year after transplantation. Although subjects do not establish immunological stability (i.e. stable T cell counts and B cell function) until almost 2 years after transplantation, the one year parameters of T cell counts, proliferative responses to antigens, T cell receptor excision circles (TRECs), and T cell receptor diversity are positive indicators of successful immune reconstitution.

3.1. Assess survival at 1 year.

3.1.1. The primary hypothesis is that greater than 50% of subjects will survive thymus transplantation.

3.2. Assess naïve CD4 T cell counts at 12 months post-thymus transplantation.

3.2.1. A secondary hypothesis is that greater than 50% of subjects will have >100 naïve CD4 T cells at one year post-transplantation.

3.2.2. Another secondary hypothesis is that the dose of thymus tissue transplanted will affect the naïve CD4 count at one year.

3.3. Perform descriptive studies.

3.3.1. Tabulate immune outcomes at 12 months.

3.3.2. Tabulate the presence of donor T cells in the blood at 3 months post transplantation.

3.3.3. Tabulate graft versus host disease in first 12 months post transplantation.

3.3.4. Tabulate infection rates in first 12 months post transplantation.

3.3.5. Tabulate autoimmune disease in first 12 months post transplantation.

3.3.6. Tabulate persistent rashes present in first 12 months post transplantation.

3.3.7. Tabulate other adverse events that are possibly, probably or definitely related to the thymus transplant detected in first 12 months post transplantation.

4. Trial Design.

4.1. Primary and secondary endpoints.

4.1.1. Primary endpoint.

4.1.1.1. Survival at 1 year after transplantation. Survival at 2 years after transplantation will be analyzed as supportive data.

4.1.2. Secondary endpoints include the following, as data permit.

Secondary Endpoints (at year 1 unless otherwise specified)	
CD3 T cells	6 and 12 months

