5.1.3.1.3. To Fit the Category of *Typical* complete DiGeorge anomaly

5.1.3.1.3.1. Circulating CD3⁺ CD45RA⁺ CD62L⁺ T cells will be <50/mm³ or <5% of the total T cell count.

5.1.3.1.3.1.1. The phenotypic evaluation of T cells is done by flow cytometry.

5.1.3.1.3.1.2. Flow cytometry must be performed twice.

5.1.3.1.3.1.3. Two studies must show similar immunological findings.

5.1.3.1.3.1.4. One assay must be done within 3 months of transplantation.

5.1.3.1.3.1.5. One assay must be within 1 month of transplantation.

5.1.3.1.3.1.6. These assays will be done in a Clinical Laboratory Improvement Amendments (CLIA) Certified Laboratory, or a College of American Pathologist (CAP) Certified Laboratory.

5.1.3.1.3.2. PHA proliferative response.

5.1.3.1.3.2.1. For Group 1.

5.1.3.1.3.2.1.1. T cell proliferative response to PHA of <5,000 cpm or less than 20 fold above background.

5.1.3.1.3.2.2. For Group 2.

5.1.3.1.3.2.2.1. T cell proliferative response to PHA of > 5,000 cpm and <50,000 cpm or >20 fold over background.

5.1.3.1.3.2.3. For Group 3.

5.1.3.1.3.2.3.1. T cell proliferative response to PHA of >50,000 cpm.

5.1.3.1.3.2.4. For all three Groups, two assays of T cell numbers and PHA responses must show similar immunological findings (eg both must meet criteria).

5.1.3.1.3.2.4.1. One assay must be done within 3 months of transplantation.

5.1.3.1.3.2.4.2. One assay must be done within 1 month of transplantation.

5.1.3.1.3.2.4.3. Assays will be done in a CLIA or CAP Certified Laboratory.

5.1.3.1.3.3. Optional tests in subjects with typical complete DiGeorge anomaly.

5.1.3.1.3.3.1. TRECS (T cell receptor rearrangement excision circles)

5.1.3.1.3.3.1.1. TREC_s are not assayed prior to transplantation.

5.1.3.1.3.3.1.2. Newborn screening or other TREC data, if available,

may be recorded.

5.1.3.1.4. To Fit the Category of *Atypical* complete DiGeorge anomaly.

5.1.3.1.4.1. Rash.

5.1.3.1.4.1.1. The subject must have, or have had, a rash. If the rash is present, a biopsy of the rash must show T cells in the skin. If the rash and adenopathy have resolved, the subject must still have $>50/\text{mm}^3$ T cells and the naive T cell (CD45RA $^+$ CD62L $^+$ CD3 $^+$ T cells) count must be $<50/\text{mm}^3$ or $<5\%$ of the T cells.

5.1.3.1.4.1.2. Usually there is lymphadenopathy. If the rash has just developed, the subject may not yet have lymphadenopathy.

5.1.3.1.4.2. PHA proliferative response.

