6.2.1.8.3.11.1. If new rashes develop, the rash will be monitored daily (while the subject is at DUMC).

6.2.1.8.3.11.2. Biopsies will be taken on rashes that are severe and persist for more than 2 weeks to assess the etiology of the rash. If granuloma are found, evidence for sarcoidosis including an angiotension converting enzyme (ACE) level and eye examination will be sought.

6.2.1.8.3.12. Diarrhea.

6.2.1.8.3.12.1. If severe diarrhea develops, endoscopy and colonoscopy will be done as indicated with biopsies to assess for the etiology of the diarrhea.

6.2.1.8.3.13. Endocrine studies.

6.2.1.8.3.13.1. Thyroid Studies.

6.2.1.8.3.13.1.1. Thyroid function studies will be done to screen for thyroid disease.

6.2.1.8.3.13.1.2. Anti-thyroglobulin and anti-thyroid peroxidase antibodies will be measured if the subject develops thyroid disease.

6.2.1.8.3.13.1.3. Thyroid function studies will be done as follows

- Month 6 ± 1 month
- Month 12 ± 2 months

6.2.1.8.3.13.1.4. If thyroid disease develops, the endocrine evaluation is directed by the subject's endocrinologist or primary care physician.

6.2.1.8.4. Testing for medical conditions.

6.2.1.8.4.1. Medically indicated studies are done as necessary and may include the following

6.2.1.8.4.1.1. Laboratory studies, for example, ionized calcium, magnesium, blood counts, and/or cultures.

6.2.1.8.4.1.2. Calcium.

6.2.1.8.4.1.2.1. For subjects on calcium supplementation

6.2.1.8.4.1.2.2. Serum calcium levels will be done monthly for 1 year.

6.2.1.8.4.1.2.3. Urine calcium/creatinine ratio will be done as follows

- Months 1, 2, 3, 4, 5, 6
- Months 9 and 12
- As medically indicated

6.2.1.8.4.1.3. Periodic cardiac evaluation(s) as recommended by the subject's cardiologist.

6.2.1.8.4.1.4. Endocrinology may recommend additional test(s).

6.2.1.8.4.1.5. Follow up renal ultrasound(s) may be done.

6.2.1.8.5. Safety Testing.

6.2.1.8.5.1. CMV testing of blood by PCR and EBV by PCR

- Month 3 ± 1 month

6.2.1.8.6. Physical Examination.

6.2.1.8.6.1. Physical examinations will be done monthly.

6.2.1.8.6.1.1. The length of the subject is recorded, as autoimmune thyroid

disease can first be detected when the length stops increasing.

6.2.1.8.6.1.2. The subject will be observed for the development of new rashes that are severe and persist for more than 2 weeks.

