8.1.1.1.1. Subjects are monitored for signs of rashes and/or infection, such as

fever, etc. If a fever develops, the subject is assessed by blood and other cultures and treated with antibiotics as medically indicated.

8.1.1.1.2. DUHS and Clinical Care Unit Infection Control policies are followed while at Duke.

8.1.1.2. GVHD.

8.1.1.2.1. Chimerism studies on circulating T cells are performed at 3 ± 1 month after transplantation to detect thymus donor T cells.

8.1.1.2.2. If clinical symptoms resembling those of GVHD develop, the relevant tissue is biopsied and examined by DUMC pathology. Blood will be tested to determine if the T cells are recipient, maternal, or thymus donor. GVHD will be treated, if medically indicated, by standard approaches.

8.1.1.3. Infection.

8.1.1.3.1. Infection information during the first 24 months post transplantation is requested from the primary and or referring physician.

8.1.1.4. Autoimmune disease.

8.1.1.4.1. Autoimmune disease is recorded for the first 24 months post transplantation.

8.1.1.5. Malignancy.

8.1.1.5.1. Development of a malignancy is always a possibility in patients with poor T cell function. EBV and CMV-related lymphomas have been reported in the past (Dictor et al 1984; Borzy et al 1979).

8.1.1.5.2. The recipient is tested prior to transplantation for presence of EBV or CMV to help assess the risk of lymphoproliferative disease after transplantation.

8.1.1.6. CMV Testing.

8.1.1.6.1.1. Thymus transplant recipients are tested before thymus transplantation and at Month 3 ± 1 month after thymus transplantation to screen for the presence of CMV.

8.1.1.7. EBV Testing.

8.1.1.7.1.1. Thymus transplant recipients are tested before thymus transplantation and at Month 3 ± 1 month after thymus transplantation to screen for the presence of EBV.

8.1.2. Previously observed adverse events.

8.1.2.1. Individuals with complete DiGeorge anomaly are at risk (even without therapy) from serious infections, aspiration, graft-versus-host disease from maternal cells or from unirradiated blood transfusions, death from cardiac complications, or complications from laryngomalacia. Individuals with

complete DiGeorge anomaly often develop skin rashes and cytopenias (even without therapy). For the purposes of this protocol, all pre-existing conditions are not considered adverse events and are not recorded as such. Pre-existing conditions are reported in the medical history.

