5.2 Graft versus Host Disease

In clinical studies with RETHYMIC, GVHD occurred in 11 (10%) RETHYMIC-treated patients of whom 6 (55%) died. RETHYMIC may cause or exacerbate pre-existing GVHD. Seven patients (7%) experienced autologous GVHD, 3 patients (3%) experienced GVHD due to maternal cells and 1 patient (1%) experienced GVHD due to cells from a prior hematopoietic cell transplant (HCT). Risk factors for GVHD include atypical complete DiGeorge anomaly phenotype, prior HCT and maternal engraftment. GVHD may manifest as fever, rash, lymphadenopathy, elevated bilirubin and liver enzymes, enteritis, and/or diarrhea. Patients with elevated baseline T cell proliferative response to PHA > 5,000 cpm or > 20-fold over background should receive immunosuppressive therapies to decrease the risk of GVHD (Table 2 and Table 3). Development of GVHD symptoms should be closely monitored and promptly treated.

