14 CLINICAL STUDIES

The efficacy of RETHYMIC was evaluated in 10 prospective, single-center, open-label studies that enrolled a total of 105 patients, including 95 patients in the primary efficacy analysis. The demographics and baseline characteristics of the patients enrolled in the clinical studies were similar across studies. Across the efficacy population, 59% were male; 70% were White, 22% were Black, 4% were Asian/Pacific Islander; 2% were American Indian/Alaskan Native; and 2% were multi-race. The median (range) age at the time of treatment was 9 months (1-36). The diagnosis of congenital athymia was based on flow cytometry documenting fewer than 50 naïve T cells/mm³ (CD45RA⁺, CD62L⁺) in the peripheral blood or less than 5% of total T cells being naïve in phenotype in 91/95 patients (range 0-98 naïve T cells/mm³). In addition to congenital athymia, patients also had complete DiGeorge syndrome (cDGS; also referred to as complete DiGeorge anomaly (cDGA)) if they also met at least one of the following criteria: congenital heart defect, hypoparathyroidism (or hypocalcemia requiring calcium replacement), 22q11 hemizygosity, 10p13 hemizygosity, CHARGE (coloboma, heart defect, choanal atresia, growth and development retardation, genital hypoplasia, ear defects including deafness) syndrome, or CHD7 mutation. Across the efficacy population, 93 patients (98%) were diagnosed with cDGS, and the most common DiGeorge gene mutations or syndromic associations were Chromosome 22q11.2 deletion (36 patients; 38%) and CHARGE syndrome (23 patients; 24%). There were 35 patients with missing or no identified genetic mutations. Two (2%) patients had FOXN1 deficiency, and 1 patient (1%) had a TBX variant. There were 50 (53%) patients with typical cDGS; these patients had congenital athymia with the absence of a T cell-related rash. There were 42 (44%) patients diagnosed with atypical cDGS; these patients may have had a rash, lymphadenopathy, or oligoclonal T cells. Patients who did not have congenital athymia (e.g. SCID) and patients with prior transplants, including thymus and HCT, were excluded from the efficacy analysis population. The baseline demographics and disease characteristics were similar in the safety population.

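### Protocol 8.1.2.1 keeps pre-existing conditions out of adverse-event recording, with no reference date and no rule for worsening, so a rash or GVHD carried into transplantation has no sure route into the rash and GVHD tables

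*Protocol*

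**What the plan says.** Protocol 8.1.2.1 lists risks that these children run even without therapy, among them GVHD from maternal cells or unirradiated transfusions, and skin rashes. It then rules that "all pre-existing conditions are not considered adverse events and are not recorded as such", and adds: "Pre-existing conditions are reported in the medical history".

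The objectives ask for two tables that touch these conditions. Protocol 3.3.6: "Tabulate persistent rashes present in first 12 months post transplantation". Protocol 3.3.3: "Tabulate graft versus host disease in first 12 months post transplantation". Protocol 4.1.3 and SAP 5.8.1.2 both class rashes and GVHD as adverse events of special interest (AESI).

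Rash is also part of the entry definition of atypical disease (Protocol 5.1.3.1.4.1.1): "The subject must have, or have had, a rash". At physical examination the protocol looks for new rash only (6.2.1.8.6.1.2): "The subject will be observed for the development of new rashes that are severe and persist for more than 2 weeks".

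For GVHD, the prescribing information in Appendix C, section 5.2, warns: "RETHYMIC may cause or exacerbate pre-existing GVHD".

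**The concern.** An outcome that the trial promises to report overlaps with a condition that one phenotype must have, or have had, at entry. The recording rule says that such a condition is not an adverse event, and the outcome tables are built from adverse events. Suppose an atypical infant enters transplantation with an active rash that lasts for months or spreads. One abstractor, following 8.1.2.1, leaves it in medical history. Another, following 3.3.6 or 8.3.3.1, records it. Both can cite the protocol.

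The interpretation of rash and GVHD in atypical subjects is at stake. A low rate could reflect the graft or the recording rule, and the tables would not show which. Worsening of carried-in GVHD, a risk the product's own labelling names, would have no defined place in the adverse-event output.

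**Working it through.** The plan states no figure for this point, so the check is mainly a comparison of texts.

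**1. What each section does with a rash present at transplantation**

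| Section | Effect |
|---|---|
| Protocol 8.1.2.1 | Not an adverse event; medical history only |
| Protocol 3.3.6 | Counts it if it persists, since the objective concerns rashes present, not rashes that began |
| Protocol 8.3.3.1 | Can be read to count it, since the definition covers any unwanted experience during the trial |
| Protocol 8.3.2.3.3 | Counts it if it lasts more than two weeks; no new-onset limit, but only after discharge from Duke |
| Protocol 6.2.1.8.3.11.1 and 6.2.1.8.6.1.2 | Does not follow it; both concern new rashes |
| SAP 5.8.1.2 | Counts it only if it was recorded as an adverse event |

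**2. Is there an exception for worsening?** None appears in Protocol 8.1.2.1, 8.3.2 or 8.3.3, or in SAP 5.8.1. The SAP does not define a treatment-emergent adverse event. No section says whether pre-existing refers to consent, enrolment or transplantation.

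**3. Do the tables depend on adverse-event records?** Yes. The SAP's planned outputs for rash and GVHD are the AESI tables by system organ class and preferred term (Tables 14.3.1.10 and 14.3.1.10.2). SAP 6.3 lists no other rash or GVHD table. Protocol 3.3.7 follows with *other* adverse events, which implies that 3.3.3 to 3.3.6 are adverse-event tabulations too. The medical history table (14.1.6.1) has no stated post-transplant grade or change.

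**4. Can a carried-in rash plausibly persist?** Protocol 2.3.1.2.2 describes rash as a risk that runs from before transplantation into the first months after it, and reports that it resolved once naïve T cells developed. Appendix C, section 12.1, says that naïve T cells are unlikely to be seen before 6 to 12 months. Persistence beyond two weeks is therefore plausible, though no frequency is given.

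**5. GVHD.** The atypical entry criteria do not include it. Protocol 8.1.2.1 ties it to maternal cells or unirradiated transfusion. Maternal engraftment is admitted in typical subjects (Group 3) and atypical subjects (Groups 3 and 4). In Appendix C, section 5.2, 3 of the 11 GVHD cases came from maternal cells: 3/105 = 2.9% of the pooled population. That figure does not say how many were present before transplantation.

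**6. Scale.** Appendix C, section 14: "There were 42 (44%) patients diagnosed with atypical cDGS", in an efficacy population of 95.

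- 42/95 = 44.2%, which agrees with the stated 44%.
- Lower bound for rash: 0%, if no atypical subject had an active rash at transplantation or if all were recorded despite 8.1.2.1.
- Upper bound for rash: about 44%, if the pooled mix applies to this study and every atypical subject carried in a rash that went unrecorded.
- SAP Table 2.1 lists 24 subjects for this study, so the upper bound would be 24 × 42/95 = 10.6, or about 11 subjects.

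The upper bound is a ceiling, not an estimate. The criterion admits past rash, and Appendix C describes atypical patients as ones who may have had rash, lymphadenopathy or oligoclonal T cells.

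**The case against.** The strongest reply is that the protocol already collects what is needed. Section 8.3.2.3.3 requests information on rashes lasting over two weeks at Months 3, 6, 12 and 24, under an adverse-event heading and without a new-onset limit. Section 8.1.1.1.1 has subjects monitored for signs of rash. The definition in 8.3.3.1 is wide enough to cover a worsening. Appendix C, section 5.3, reports autoimmune events with onset up to three days before implantation, so onset before transplantation did not in itself bar recording in the pooled studies. Enrolment is closed, and Protocol 1.5 says that three subjects remain in follow-up.

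Much of this stands, and it rules out several stronger readings:

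- A reader might infer that entry rashes are simply missing from the tables. The documents show a conflict between sections, not a proven omission.
- A reader might infer that atypical subjects will look freest of rash and GVHD. The pooled data in Appendix C do not support this: section 5.2 names atypical phenotype as a GVHD risk factor.
- A reader might extend the point to worsening infection or liver involvement. Protocol 8.1.2.8 says that infections are recorded, and 6.2.1.9 follows them to Month 24. AST and ALT are scheduled through Month 12, and SAP 5.8.2 summarises change from baseline and reports clinically significant treatment-emergent laboratory findings as adverse events.
- A reader might treat GVHD as a feature that atypical subjects bring in. The one atypical subject described with pre-existing GVHD belongs to protocol 884.1 (SAP Appendix 1).

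The reply does not settle the conflict. Section 8.1.2.1 is the more specific rule and is expressly framed for this protocol. Section 8.3.2.3.3 starts at discharge, and its adverse-event heading leaves it open to the same exclusion.

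**Conclusion.** The point holds as an unreconciled conflict. Section 8.1.2.1 cannot be squared with 3.3.6, 8.3.2.3.3 and 8.3.3.1, and the SAP does not say which governs the rash and GVHD tables. A rash at transplantation that persists or worsens has no sure route into them; the same applies, less often, to GVHD.

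The documents do not allow the understatement to be quantified. They give neither the number of subjects in this study with active rash or GVHD at transplantation nor a persistence rate, so any figure in percentage points would rest on invented rates. For rash, the affected share lies between none and about 44%, assuming the pooled atypical share applies. Typical subjects with maternal engraftment could add a few GVHD cases, whose number is also not given.

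With enrolment closed, the matter bears mainly on the study report. It is still worth correcting, because the rash and GVHD results in atypical subjects cannot be interpreted otherwise.

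**What to change.** Three changes:

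1. In Protocol 8.1.2.1, state that pre-existing means present before transplantation, and that an increase in grade over the last pre-transplant assessment, or a recurrence, is recorded as an adverse event dated at the worsening.
2. In the SAP, split the rash and GVHD AESI tables for study 25966 into *present at transplantation and persisting or worsened* and *new onset*. A rash that persists unchanged would still not be an adverse event, so the first class must also draw on the physical examinations and the Month 3, 6 and 12 contacts already scheduled.
3. Check the charts of atypical subjects already treated, and of any subject with maternal engraftment, so that the split can be filled in retrospectively.

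The cost is a few sentences in the protocol, one table split and the chart check. Reported rash and GVHD counts may rise somewhat. No visit, test or treatment changes.

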9.1.2.3. Of note there have been 32 subjects with complete DiGeorge anomaly who would have met entrance criteria for this protocol who have been treated under protocols 668, 884, 931, 932, or 950 and had naïve T cell counts done at 1 year \pm 2 months. Twenty five of the 32 (78%) reached the target of 100 naïve CD4 cells/mm³ at one year \pm 2 months. Thus 22% did not reach the target of 100 naïve CD4 cells/mm³. Data were similar for subjects treated with immune suppression and those not treated with immune suppression.

9.1.2.4. The statistical plan is analogous to that in 9.1.7. The results are evaluated after 8, 16 and 25 subjects reach 1 year after transplantation.

9.1.2.5. [name], biostatistician, designed the following one year naïve CD4 T cell count stopping rules. The year one naïve CD4 T cell counts will be assessed after 8, 16, and 25 subjects reach 1 year after transplantation. For any immunosuppression group, the endpoint in this analysis is the number of naïve CD4 T cells at 12 months \pm 2 months. A count of 100/mm³ naïve CD4 T cells or less at any assessment stage is considered unacceptable. An overall acceptable prognosis is that 1/2 or less of the subjects have naïve CD4 T cells counts of 100/mm³ or less at 12 months; an unacceptable prognosis is that 2/3 or more of the subjects have naïve CD4 T cells counts of 100/mm³ or less at 12 months. Formally, the hypotheses under consideration are $H_0: q \leq 0.5$ versus $H_1: q \geq 0.67$ where q is the proportion of subjects who have naïve CD4 T cells counts of

100/mm³ or less. Since the hypothesis and the number of subjects at each evaluation stage is the same as the survival safety analysis in Section 4.6.2 the same stopping rules apply with the same Type I and II error rates. That is, stop enrollment to the trial at the three evaluation stages and conclude that the procedure is unacceptable as soon as 7 of the first 8 transplanted subjects, 11 of the first 16 transplanted subjects, or 15 of the first 25 transplanted subjects have naïve CD4 T cells counts of 100/mm³ or less at 12 months ± 2 months. The naïve CD4 count ($\leq 100/\text{mm}^3$) applies whether or not all immunosuppression has been weaned.

- 9.1.2.6. The null hypothesis, H_0 , is a good outcome and denotes that the proportion of subjects with a naïve T cell count $< 100/\text{mm}^3$ at one year after transplantation is ≤ 0.5 .

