9.1.2.15. Using the data in the Table 4 below, after 8 subjects have been transplanted, if 7 have <100 naïve CD4 cells one year \pm 2 months after transplantation, or after 16 have been transplanted and reached one year, if 11 have < 100 naïve CD4 T cells/ m^3 , or after 25 have been transplanted and reach one year, if 15 have < 100 naïve CD4 cells/ mm^3 , the protocol will be stopped and the treatment declared to be not efficacious.

Table 4: Analysis of naïve CD4 T cell outcomes for activation of stopping rule.

Stopping rule to be used				
x_1	n_1	α_1	α	β
x_2	n_2	α_2		
x_3	n_3	α_3		
7	8	0.035	0.23	0.156
11	16	0.082		
15	25	0.122		
Examples of stopping rules rejected				
6	8	0.145	0.289	0.17
10	16	0.127		
16	25	0.017*		
6	8	0.145	0.197	0.289#
11	16	0.042		
17	25	0.011#		

*Rejected because α_3 is so small can contributes little to the overall α # Rejected because β is greater than α , and α_3 is so small

9.1.3. Stopping Rule regarding survival of CMV infected subjects with typical complete DiGeorge anomaly.

9.1.3.1. The stopping rule for inclusion of CMV infected subjects will be based on the sequential probability ratio test (SPRT) designed to evaluate whether the estimated probability of survival within 12 months favors $p_1 = 0.1$ or $p_2 = 0.5$, clinically important values chosen to facilitate decisions about early stopping. The decision of stopping enrollment of this subgroup of subjects will be evaluated sequentially using the accumulating data, and enrollment of CMV infected subjects will be stopped if:

Four of 4 subjects die, otherwise

- (if 1 of the first 4 subjects survives) 7 of 8 subjects die, otherwise
- (if 2 of the first 8 subjects survive) 10 of 12 subjects die, otherwise
- (if 3 of the first 12 subjects survive) 12 of 15 subjects die, otherwise
- (if 4 of the first 15 subjects survive) 15 of 19 subjects die, otherwise (if 5 of the first 19 subjects survive) 18 of 23 subjects die, otherwise
- (if 6 of the first 23 subjects survive) 21 of 27 subjects die, otherwise
- (if 7 of the first 27 subjects survive) 23 of 30 subjects die.

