9.1.3.2. It is assumed here that no more than 30 CMV infected subjects with typical complete DiGeorge anomaly will be considered for enrollment. Under these stopping rules, there is less than 8.4 percent chance that enrollment will be stopped if the true survival rate is 50% or greater. The probability of stopping enrollment is more than 92 percent if the true survival rate is 10% and more than 55 percent if the true survival rate is 25%. These stopping rules are designed to serve as guidelines for the sponsor, and the decision to stop or continue enrollment of CMV infected subjects may depend on a variety of clinically important factors.

9.2. The number of subjects planned to be enrolled. Reason for choice of sample size, including reflections on the power of the trial and clinical justification.

9.2.1. It is anticipated that approximately 25% will die in the early post transplant course (based on past experience) from infections or other medical complications. We want sufficient numbers to assure us that we can determine whether the protocol as written will result in the development of naïve T cells without excessive adverse events.

9.3. The level of significance to be used.

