5.5 Cytomegalovirus Infection

In clinical studies with RETHYMIC, 3 out of 4 patients with preexisting CMV infection prior to treatment with RETHYMIC died. The benefits/risks of treatment should be considered prior to treating patients with pre-existing CMV infection.

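### The CMV rule's stated false-stop chance of under 8.4% is not met at exactly 50% survival: it is 8.45% if only the bracketed survivor counts are followed, 9.06% if every unstopped path stays monitored

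*Protocol*

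**What the plan says.** Protocol 9.1.3.1 sets a rule for stopping enrolment of CMV-infected subjects with typical complete DiGeorge anomaly. It is based on a sequential probability ratio test of 12-month survival of 0.1 against 0.5, and "The decision of stopping enrollment of this subgroup of subjects will be evaluated sequentially using the accumulating data". Eight death boundaries follow: 4 of 4, 7 of 8, 10 of 12, 12 of 15, 15 of 19, 18 of 23, 21 of 27 and 23 of 30. Each boundary after the first is preceded by a survivor count in brackets, for example "if 2 of the first 8 subjects survive) 10 of 12 subjects die, otherwise".

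Protocol 9.1.3.2 assumes that "no more than 30 CMV infected subjects with typical complete DiGeorge anomaly will be considered for enrollment" and gives the rule's properties. On false stopping: "there is less than 8.4 percent chance that enrollment will be stopped if the true survival rate is 50% or greater". On true stopping: "The probability of stopping enrollment is more than 92 percent if the true survival rate is 10% and more than 55 percent" at 25% survival. It adds that the rules are "designed to serve as guidelines for the sponsor".

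**The concern.** The bound in 9.1.3.2 is a strict inequality over a range of survival that includes 50%. The stopping probability falls as survival rises, so 50% is the worst case and the bound must hold there. It follows exactly from the printed boundaries, so it can be checked.

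The check also needs something that 9.1.3.1 leaves out. It does not say what happens when more subjects survive than the bracket names, for instance when 2 of the first 4 survive. Monitoring may end there or continue to the later boundaries, and no limit for ending in favour of 0.5 is printed. What is at stake is whether the rule and its stated properties can be reported correctly.

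**Working it through.** **Inputs (Protocol 9.1.3.1 and 9.1.3.2).** Looks at n = 4, 8, 12, 15, 19, 23, 27, 30. Stop if deaths reach d = 4, 7, 10, 12, 15, 18, 21, 23. Bracketed survivor counts before looks 2 to 8: 1 of 4, 2 of 8, 3 of 12, 4 of 15, 5 of 19, 6 of 23, 7 of 27. Maximum 30 subjects. Outcomes are taken as independent with a common survival probability s.

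**Method.** Let f(k) be the probability of k deaths without having stopped. For m new subjects between looks, f_new(k + x) adds f(k) · C(m, x) · (1 − s)^x · s^(m − x). The mass with deaths ≥ d is the stopping probability at that look; the rest is carried forward.

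**Reading A: only the bracketed counts are followed.** A path stays monitored only if its survivors equal the bracketed count at every look. A stop then needs all subjects since the last look to die. At s = 0.5:

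- Look 1: 0.5^4 = 0.062500
- Look 2: P(1 of 4 survives) = 4/16 = 0.25; × 0.5^4 = 0.015625
- Look 3: 0.25 × 0.25 = 0.0625; × 0.5^4 = 0.003906
- Look 4: 0.0625 × 0.25 = 0.015625; × 0.5^3 = 0.001953
- Look 5: 0.015625 × 3/8 = 0.005859; × 0.5^4 = 0.000366
- Looks 6 to 8, in the same way: 0.000092, 0.000023, 0.000011
- Sum: 0.08448

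**Reading B: every unstopped path stays monitored.** At s = 0.5 the looks contribute 0.062500, 0.015625, 0.005371, 0.004272, 0.001581, 0.000679, 0.000311 and 0.000297, a sum of 0.09064. The readings first differ at look 3. Reading B keeps paths with 2 survivors among the first 4 and none among the next 4. Of these, 6 × 0.5^12 = 0.001465 stop at 10 of 12, and 0.003906 + 0.001465 = 0.005371.

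**Results.**

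| Survival | Stated in 9.1.3.2 | Reading A | Reading B |
|---|---|---|---|
| 50% | < 8.4% | 8.45% | 9.06% |
| 25% | > 55% | 55.5% | 72.1% |
| 10% | > 92% | 92.7% | 99.7% |

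Reading A gives 8.448%, 55.49% and 92.68% before rounding. It matches the printed figures, except that 8.448% is not less than 8.4%. The stopping probability falls to 8.4% at a true survival of 50.06% under A and 50.75% under B.

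**Do the brackets decide between A and B?** Not by themselves. A path that has not stopped at one look has at least the bracketed number of survivors, and it can meet the next boundary only if it has no more than that. Take 2 survivors of 4, still 2 of 8, then 10 deaths of 12: the bracket printed before that boundary is satisfied and the boundary is met. The brackets lower the stopping probability only if they are applied as an unbroken chain.

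**Other routes to the stated figures.** The first three looks alone, with all unstopped paths monitored, give 8.35%, 52.7% and 92.4%, which fails the 25% statement. A search over lower log-likelihood-ratio limits from −6.0 to −0.5 for accepting 0.5 found none that meets all three statements. The nearest coincides with reading A; the next tighter limit gives 7.90%, 49.5% and 85.9%.

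**The case against.** The best defence is that reading A was meant. The brackets are printed as part of the rule, and reading B leaves them without effect. A sequential probability ratio test normally also has a limit at which it ends in favour of the better hypothesis, and the chain behaves that way. All three printed figures fit the chain. The only fault is then that the words less than were attached to a value rounded down, and the bound fails only for survival between 50% and about 50.06%.

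Most of this stands. Reading A is very probably how the figures were computed, and a reader should not infer that 9.06% is what the rule says as written: the brackets are written too. What does not go away is that the strict bound is untrue even on reading A, and that 9.1.3.1 never says that monitoring ends when survivors exceed the bracketed count.

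A reader might also infer that the gap at 25% survival (55.5% against 72.1%) shows a misstated power. It does not. It compares two readings, and the printed figures for 25% and 10% survival are lower bounds that hold under both.

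On impact, the objection is right. Protocol 4.6 notes that the study is closed to enrolment, and 9.1.3.2 makes the rule advisory. Both readings give 0.0625 + 0.015625 = 7.81% at 50% survival through 8 subjects. The label in Appendix C, section 5.5, reports that "3 out of 4 patients with preexisting CMV infection prior to treatment with RETHYMIC died", so pre-existing CMV infection was seen in only 4 patients across the clinical studies.

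**Conclusion.** The false-stop bound in 9.1.3.2 is wrong as printed. At 50% survival the excess over 8.4% is 0.05 points if only the bracketed counts are followed and 0.66 points if every unstopped path stays monitored. On the first reading, which the printed figures favour, this is a rounding slip. The text of 9.1.3.1 does not settle which reading applies.

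The result rests on the printed boundaries, a maximum of 30 subjects, and independent outcomes with a common survival probability. It is exact under those assumptions. It does not show that the boundaries are unsuitable, or that any enrolment decision was affected. It is a minor correction to a stated property of a decision rule.

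**What to change.** 1. Add one sentence to 9.1.3.1 saying whether monitoring ends once survivors exceed the bracketed count.
2. Restate 9.1.3.2 to match:
   - If monitoring ends there: less than 8.5 percent at 50% survival or above. The statements for 25% and 10% survival can stay as they are.
   - If monitoring continues: less than 9.1 percent at 50% survival or above, more than 72 percent at 25% and more than 99 percent at 10%.

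The cost is a text correction. No boundary changes and there is no effect on enrolment. The printed bound becomes 0.1 or 0.7 points less favourable, depending on the reading.
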